**NOTE: IF YOUR STUDY INVOLVES:** 

Genetic Testing | Blood Draws

MRI scans

resident, fellow or other trainee)

#### **Investigator Interests:**

Does the principal investigator, or do any research personnel who are responsible for the design, conduct or reporting of this project or any of their family members (spouse or dependent child) have an incentive or interest, financial or otherwise, that may affect the protection of the human participants involved in this project, the scientific objectivity of the research or its integrity? Note: The Principal Investigator (Project Director), upon consideration of the individual's role and degree of independence in carrying out the work, will determine who is responsible for the design, conduct, or reporting of the research.

See Disclosures and Management of Personal Interests in Human Research				
http://www.yale.edu/hrpp/policies/index.html#COI				
□ Yes □ No X				
Do you or does anyone on the research team who is determined by you to be responsible for the design, conduct or reporting of this research have any patent (sole right to make, use or sell an invention) or copyright (exclusive rights to an original work) interests related to this research protocol?  Yes  No X				
If yes to either question above, list names of the investigator or responsible person:				

The Yale University Principal Investigator, all Yale University co-investigators, and all Yale University individuals who are responsible for the design, conduct or reporting of research must have a current financial disclosure form on file with the University's Conflict of Interest Office. Yale New Haven Hospital personnel who are listed as co-investigators on a protocol with a Yale University Principal Investigator must also have a current financial disclosure form on file with the University's Conflict of Interest Office. If this has not been done, the individual(s) should follow this link to the COI Office Website to complete the form: http://www.yale.edu/coi/

NOTE: The requirement for maintaining a current disclosure form on file with the University's Conflict of Interest Office extends primarily to Yale University and Yale-New Haven Hospital personnel. Whether or not they are required to maintain a disclosure form with the University's Conflict of Interest Office, all investigators and individuals deemed otherwise responsible by the PI who are listed on the protocol are required to disclose to the PI any interests that are specific to this protocol.

## **SECTION II: GENERAL INFORMATION**

1. **Probable Duration of Project:** State the expected duration of the project, including all follow-up and data analysis activities.

**36 months:** Expected start date: 04/01/2016; Expected End Date: 06/31/2019.

2. **Study location:** State where the study will take place and in what setting. If international, complete and submit International checklist (http://www.yale.edu/hrpp/forms-templates/behavioral.html) Note: If your research involves interactions with any embargoed countries you should contact the Director of Corporate Contracts and Export Control Licensing ([contact] or call [contact]) for guidance on how to proceed.

This first part of this study consists of focus groups and interviews that will be conducted inperson and by telephone and an intervention that will be conducted online with participants recruited from South and Central Appalachia (Southern West Virginia, Eastern Kentucky, Western Virginia, Eastern Tennessee). In-person focus groups will be conducted at East Tennessee State University in [name] research office in the Department of Psychology.

During the second part of this study, we will test a writing intervention online. Data analysis will occur at Yale University in New Haven, CT (PI [name]), College of the Holy Cross in Worcester, MA (PI [name]), and East Tennessee State University in Johnson City, TN (Subaward PI [name]).

3.	Help us categorize your research! Are you using any of the following?
	Class Project
	Participant Observation
	⊠Interviews
	⊠Surveys
	⊠ Focus groups (study is not anonymous)
	Research in K-12 schools (submit a School Agreement form for the study)
	Deception (submit a Debriefing sheet)
	Audiotaping, videotaping or photography of individuals (study is not anonymous)
	Public viewing of videotapes or photographs
	Yale Psychology Pool (study does not qualify for exemption)
	International research sites (attach the International Checklist)
	⊠Online (web-based) activities
	Social networks

## **SECTION IV: RESEARCH PLAN**

1. **Statement of Purpose:** State the scientific aim(s) of the study, or the hypotheses to be tested.

*Aim 1 (Conduct elicitation research, phase 1):* 

We will conduct focus groups and structured interviews with 20 rural lesbian, gay, and bisexual (LGB) emerging adults and LGB community leaders in order to create appealing, culturally resonant intervention materials for rural Appalachian LGB emerging adults (aged 18-29 years).

Aim 2: (Use elicitation research findings to adapt interventions, phase 2):

We will interview 10 LGB emerging adults and LGB community leaders to further refine

Expressive Writing (EW), Self-Affirmation (SA), and Control (C) online writing interventions for use among LGB emerging adults in rural Appalachia.

Aim 3: (Intervention feasibility, acceptability, and preliminary efficacy testing, phase 3):

We will examine the feasibility, appeal, and preliminary efficacy of EW and SA interventions relative to control. The primary outcomes of interest will include depressive symptoms, suicidality, substance use, and HIV sexual risk behaviors at the 3-month post-intervention assessment.

2. **Background:** Describe the background information that led to the plan for this project. **Provide references** to support the expectation of obtaining useful scientific data.

Lesbian, gay, and bisexual (LGB) emerging adults (ages 18-29) report significantly greater depression, suicidality, substance use, and HIV risk behaviors than heterosexuals (1,2). These disparities are magnified among LGB emerging adults who live in rural or nonurban areas in the US (3). Indeed, rural LGB emerging adults are more likely to binge drink, use illegal drugs, and report depression than their urban LGB peers (4,5). These disparities are particularly severe in Appalachia, a cultural context characterized by negative attitudes and interpersonal discrimination towards LGBs (6,7), mental and physical health outcomes among the poorest in the nation (8), and limited access to mental and physical health providers (9).

This proposal is designed to adapt and test the feasibility and efficacy of online Expressive Writing (EW) and Self-Affirmation (SA) writing interventions that offer two low-cost, portable vehicles capable of mitigating mental health and behavioral risk disparities among Appalachian LGB emerging adults.

1. Expressive Writing (EW) interventions prompt individuals to write about personally stressful events, enabling cognitive-affective stress processing. Our own pilot work and other recent

- studies demonstrate that EW reduces depression (10) and alcohol and illicit drug use (11, 12) and can, in combination with other techniques, reduce HIV sexual risk (13) among urban LGB emerging adults.
- 2. Self-Affirmation (SA) writing interventions prompt individuals to write advice to a (hypothetical) and similarly stigmatized person regarding how best to cope with stigmarelated stress. By affirming one's own stigmatized identity through the process of helping another similarly stigmatized person (14, 15), SA has been shown to reduce alcohol use (11) and stress hormones (e.g., cortisol) (16,17) closely associated with depression among emerging adults.

In this exploratory research project, we propose to adapt and test the comparative efficacy of these brief, low-cost, and portable interventions to improve mental health and health risk behaviors among Appalachian LGB emerging adults, one of the most vulnerable populations in the U.S. Moreover, we apply Minority Stress Theory (18) to identify and test two plausible mechanisms through which EW and SA might mitigate mental and behavioral health disparities faced by LGB individuals.

We propose that sexual minority stressors increase *psychobiological stress* and deplete emotional and behavioral *self-regulation*, thereby contributing to LGB disparities. Previous research has speculated (but not tested) that EW and SA interventions are effective because they reduce *psychobiological stress* and improve emotional and behavioral *self-regulation*, respectively. Therefore, in a novel test of these hypotheses, our pilot study will directly examine psychobiological stress and self-regulation as the putative mechanisms by which EW and SA interventions are efficacious and by which LGB disparities are generated.

To accomplish these research goals, this project will pursue the following aims:

**Specific Aim 1:** Conduct elicitation research with 20 Appalachian LGB emerging adults and LGB community leaders in order to develop effective intervention materials and stress targets. Participants will be asked to describe the type and frequency of sexual minority stressors faced by LGB emerging adults in their region (to create EW prompts and SA vignettes) and strategies to enhance the LGB-affirmative look-and-feel of the Phase 3 online platform.

**Specific Aim 2:** Present Specific Aim 1 results to 10 Appalachian LGB emerging adults and LGB community leaders to refine the EW prompts and SA vignettes and the LGB-affirmative, culturally relevant look-and-feel of the online platform. Identify, with these leaders, the most effective venues and materials for participant recruitment and retention, and identify the most effective modalities for future intervention dissemination.

**Specific Aim 3:** Pilot test feasibility and efficacy of writing interventions. 108 Appalachian LGB emerging adults will be randomized to complete one of three writing interventions (EW, SA, Control). They will be asked to complete outcome measures (depressive symptoms, suicidality, use of alcohol and illicit drugs, HIV risk behavior) and measures of proposed mediators (self-reported and biological stress, behavioral and emotional self-regulation) and moderators (e.g., social support,

identity centrality) at baseline, post-intervention, and three-month follow-up. In addition, structured interviews with 15 intervention participants will be used to refine study procedures as we scale up this intervention for a future RCT. Primary analyses will determine efficacy; secondary analyses will determine the moderating role of social support, gender, and other psychosocial factors (e.g., baseline risk) and estimate the effect sizes of the mediators of intervention efficacy for use in a subsequent RCT to determine the long-term efficacy and mechanisms of these interventions.

Despite evidence indicating that mental and physical health disparities are most severe among LGB emerging adults living in rural areas of the U.S., there are currently no evidence-based psychological interventions designed to mitigate sexual minority stress effects among this population (19). The proposed culturally-relevant, theory-based interventions are poised to reduce this gap and, therefore, address one of the most pressing public health goals of the U.S. Department of Health and Human Services (20, 21).

We will conduct focus groups with 20 Appalachian LGB emerging adults and LGB community leaders to create culturally relevant intervention materials that can be feasibly implemented in rural contexts. We will utilize elicitation research findings from Aim 1 to adapt Expressive Writing (EW), Self-Affirmation (SA, and Control (C) online writing interventions for use among rural LGB emerging adults in rural Appalachia. Interviews with 10 Appalachian LGB emerging adults and LGB community stakeholders will additionally inform the intervention content as well as recruitment strategies. Finally, we will examine the efficacy of EW and SA relative to C. The primary outcomes of interest will include depressive symptoms, suicidality, substance use, and HIV risk behaviors at 3-month post-intervention.

#### PHASE/AIM 1:

For phase 1, we will recruit 20 rural LGB emerging adults (aged 18-29) and LGB community leaders who (i) self-identify as LGB, and (ii) currently live in South or Central Appalachia. We will recruit participants for a focus group of up to five participants through postings and ads on geo-targeted websites (e.g., Craigslist, Facebook), bulletin boards and listservs at regional colleges and universities (e.g., gay-straight alliance [GSA] listserv); and in-person announcement and flyers at local community centers, bars, and the GSA of area schools. After emailing/calling our research team, potential participants will speak with a trained research assistant (RA) who will explain the study purpose and procedures, verify eligibility, and assess consent. Age eligibility will be verified by photo ID, requiring each participant to email a snapshot of themselves holding their photo ID (note: age criterion applies only to the emerging adults, not to the LGB community leaders). Participants will use their phone to

email a photo of their IDs and these emails will be securely on Yale Secure box after received and then the record of the photo will be deleted from research staff emails after the photo is verified and stored. In our experience, an LGB sexual orientation identity is difficult to fake, especially in interviews such as ours that assess LGB cultural knowledge and contexts specific to LGB individuals.

We will aim to conduct four focus groups of five participants each (20 total participants). Two of the focus groups will be comprised of LGB emerging adults and two of the focus groups will be comprised of the LGB community leaders (LGB community leaders have already indicated their support for this Phase with letters of support on file for NIH funding application). These community leaders live in the targeted geographic region and are affiliated with an online- or community-based organization that provides support services to Appalachian LGB emerging adults. Community leaders were recruited to advise this study through in-person invitations to local LGB advocates and health providers in [name] professional network (e.g., ETSU GSA, Northeast State GSA, PFLAG Tri-Cities, Tennessee Equality Project).

If Phase 1 eligible participants are not available to come in for an in-person focus group, they will have the option to do a phone interview for Phase 1 or, alternatively, will be invited to participate in Phase 2 or Phase 3.

Drs. [name], [name], and [name] will conduct the focus groups, with the aid of research assistants. Participants will be presented with information about the preliminary goals of the intervention and will be asked to describe the type and frequency of sexual minority stressors faced by LGB emerging adults in their region (to create EW prompts and SA vignettes) and strategies to enhance the LGB-affirmative look-and-feel of the Phase 3 online writing session. Phase 1 participants will not be eligible for Phase 3, however five of the 10 LGB community leaders will be invited back to participate in Phase 2.

All focus groups will be audiotaped and transcribed by a trained research assistant or professional transcription company. Drs. [name], [name], and [name] will use thematic coding to analyze data and identify overarching assertions for modifying the SA intervention using qualitative data analysis software (e.g., NVivo, Atlas.ti). Data will be indexed and coded using open and axial coding. Axial coding will address research questions guiding our interview, while open coding will identify themes emerging from participants' perspectives. The investigative team will review Phase 1 codes to create EW prompts and SA intervention vignettes, and ensure LGB-affirmative look-and-feel of the online intervention materials and platform.

#### PHASE/AIM 2:

We will conduct 10 in-person interviews with LGB emerging adults and LGB community leaders to further refine Expressive Writing (EW), Self-Affirmation (SA), and Control (C) online writing interventions for use among rural LGB emerging adults in rural Appalachia.

After incorporating Phase 1 feedback, the intervention materials will be presented to five LGB emerging adults (not repeat participants from Phase 1) and five LGB community

leaders (repeat participants from Phase 2) (LGB community leaders have already indicated their support for this Phase with letters of support on file for NIH funding application), in order to further gather, through interviews with Drs. [name], [name], and [name], adaptations that appeal to the community for whom this intervention will ultimately be disseminated. These community members and leaders will also describe the acceptability of the intervention dosage and the most effective modalities for future intervention dissemination (see Appendix). These community leaders meet the eligibility criteria and are affiliated with an online- or community-based organization that provides support services to Appalachian LGB emerging adults. Community leaders were recruited to advise this study through in-person invitations to local LGB advocates and health providers in [name] professional network (e.g., ETSU GSA, Northeast State GSA, PFLAG Tri-Cities, Tennessee Equality Project). Phase 2 enrollment and interview materials will follow those described for Phase 1 (see Appendix).

#### PHASE/AIM 3:

We will recruit 108 Appalachian LGB emerging adults (36 per group) who (i) are aged 18-29, (ii) self-identify as a sexual minority (e.g., lesbian, gay, bisexual, pansexual, queer), (iii) currently live in Eastern Tennessee counties of Washington, Sullivan, Carter, Unicoi, Greene, or Hawkins County, and (iv) have daily personal internet access. Participants will be recruited, screened, and consented for an online writing intervention using Phase 1 strategies. Recruited individuals will be directed to complete a brief online screener gauging eligibility where they will consent to share their information with the research team. Those who consent to the online screener and meet the study eligibility criteria will then receive a call from a research team member who will share additional information about the study and gain consent for study participation. During the consent call, study staff will confirm participant age, contact information (such as phone number and address), and give participants the option to provide a secondary contact. After providing consent, participants will be emailed a link to complete an online baseline assessment (Study Task 1), then randomized to one of the three online writing interventions to be completed daily for three days starting the Monday of the following week (Study Task 2-Study Task 4). Participants will have up to two weeks to complete the three days of writing prompts. If the participant has not begun their first writing day (Study Task 2) within 24 hours of receiving the prompt than they will receive one email reminder per day for three days encouraging them to complete their writing prompt. If they still have not completed their writing prompt by the fifth day, then a research team member will try calling or texting the participant to remind them to complete the task. Upon completion of the first writing day (Study Task 2), the participant will have 24hrs to complete the second writing day (Study Task 3). If the participant does not complete the second writing day (Study Task 3) within 24 hours, then study staff will use the same email, text, and call reminder system as with writing day one (Study Task 2) to encourage them to complete writing day two (Study Task 3). The same communication and reminder protocol will be followed to encourage the participant to complete the third writing day (Study Task 4). Cumulatively, participants will have 14 days to complete the three writing prompts, but participants will not be invited to move on to the second writing prompt without first completing the prompt from writing day one, nor will they be prompted to complete the third writing task without submitting the second writing task. Seven days after completing their final writing task, or seven days after the close of the

two week writing window participants will be emailed a link to complete the post-intervention survey (Study Task 5). 30 days after completion of the first survey, and 30 days after completing the 3-month online follow-up assessment survey, participants will be mailed materials to collect a hair sample in order to assay for cortisol. At 3 months after completion of the post-intervention survey, participants will receive and complete a follow-up assessment via online survey. Lastly, we will randomly select 15 participants from Phase 3 for a follow up one-hour phone or internet-based interview where we will ask about participant experience with the writing sessions.

# **Expressive Writing (EW) Intervention:**

In the Expressive Writing (EW) intervention, participants will be instructed to continually write for 20 minutes in a free-form manner about the most stressful or traumatic LGBT+ related event that they have encountered across three, ideally, consecutive days. The EW writing prompt will ask the participant to expressively write about their most personally stressful minority stress event. As part of the prompt, common examples facing Appalachian LGBT+ emerging adults will be provided based on Phase 1 and Phase 2 feedback.

# **Self-Affirmation (SA) Intervention:**

The Self-Affirmation (SA) intervention will ask participants to read a brief description, over the course of 3 writing days, of a (hypothetical) LGBT+ youth who is facing stigma-related stress. Each day's description will contain a different LGBT+ youth facing a different stigma-related stressor derived from Phase 1 and Phase 2 interviews. Drawing on their personal experiences, participants will then be asked to write a letter for 20 minutes to advise the LGBT+ youth how best to cope with stigma-related stress. The youth description and his or her stigma-related stress experiences will be developed using Phase 1 and Phase 2 input. The gender, race/ethnicity, and sexual orientation of the described LGBT+ emerging adult will match that of the participant.

#### **Control (C) Intervention:**

Participants randomly assigned to the control condition will be asked to write about what they have done since waking up that morning for 20 minutes across 3 Writing Days. This mundane control matches the time and activity of the EW and SA arms.

The online program that captures participants' writing will ensure that each participant writes for 20 minutes by not allowing the participant to advance until 20 minutes have passed. After each writing session, participants will be provided with the contact information of a local mental health resource center and a research assistant will review each submission within 24 hours to ensure each participant's safety. If participant expresses intentions of self-harm or harm towards others the research assistant will contact 911 in the Eastern Tennessee region. PI [name], a licensed clinical psychologist, will also contact participants who indicate threat to self or others or severe emotional distress.

Drs. [name] and [name] will train a graduate research assistants at ETSU to administer the consent process, tracking database, and online intervention systems. Phase 3 assessments

and interventions will be delivered via Qualtrics.com, for which Yale University has an ongoing subscription. Research assistants will be trained to check the account once per day to ensure the safety of participants by reviewing their writing and to send reminder emails, text messages, and calls to participants who skipped a day. Drs. [name] and [name] will perform biweekly review of all systems to verify RA protocol adherence.

4. **Participant Population:** Provide a detailed description of the types of participants who will be recruited into this study.

Participants in this study will be Appalachian sexual minority (LGBTQ+) emerging adults who (i) are aged 18-29, (ii) self-identify as LGBTQ+, and (iii) currently live in Eastern Tennessee counties of Washington, Sullivan, Carter, Unicoi, Greene, or Hawkins County. (Note: there is no age-restriction for the pre-identified community leaders/stakeholders in Phase 1 and Phase 2.)

Phase 1 and Phase 2 LGBTQ+ community leaders will meet the above criteria (with the exception of age) and are also affiliated with an online- or community-based organization that provides support services to Appalachian LGBTQ+ emerging adults. Community leaders were recruited to advise this study through in-person invitations to local LGBTQ+ advocates and health providers in [name] professional network (e.g., ETSU GSA, Northeast State GSA, PFLAG Tri-Cities, Tennessee Equality Project). LGBTQ+ community leaders have already indicated their support for this project and we have their letters of support on file for the NIH funding application.

For Phase/Aim 3, participants must also have access to a minimum of 20 minutes per day of uninterrupted personal internet access.

5. **Describe** how access to the population will be gained in the study.

We will recruit participants for a focus group or individual interviews through postings and ads on geotargeted websites (e.g., Craigslist, Facebook, Reddit), bulletin boards and listservs at regional colleges and universities (e.g., gay-straight alliance [GSA] listserv); and in-person announcement and flyers at local community centers, bars, and the GSA of area schools. After completing the online screener, potential participants will be contacted by a trained research assistant (RA) who will explain the study purpose and procedures, verify eligibility, and assess consent. Age eligibility will be verified by photo ID, requiring each participant to email a snapshot of themselves holding their photo ID. In our experience, an LGB sexual orientation identity is difficult to fake, especially in interviews such as ours that assess LGB cultural knowledge and contexts specific to LGB individuals.

6. **Participant classification:** Check off all classifications of participants that will be specifically recruited for enrollment in the research project. Will participants who may require additional safeguards or other considerations be enrolled in the study? If so, identify the population of participants requiring special safeguards and provide a justification for their involvement.

Ecc Dec Yal Oth	ildren onomically disadvantagosisionally Impaired le Students ner vulnerable populati ychology Pool	Employees	

☐ Non-English Speaking

☐ Pregnant women

	Prisoners
	* *	_	children who are wards of the cy 310.4 for further requirement	*
	clusion/Exclusion Cri clusion?	teria: What are the cri	teria used to determine partici	pant inclusion or
Participants in this study will be Appalachian lesbian, gay, and bisexual (LGB) emerging adults who (i) are aged 18-29, (ii) self-identify as a sexual minority (LGBTQ+), and (iii) currently live in Eastern Tennessee counties of Washington, Sullivan, Carter, Unicoi, Greene, or Hawkins County. For Phase/Aim 3, participants must also (iv) and have access to a minimum of 20 minutes per day of personal internet access. (Note: there is no agerestriction for the pre-identified community leaders/stakeholders in Phase 1 and Phase 2.)				
		-	ers have already indicated the on file for the NIH funding app	1.1

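### The mental health contact is described only as following each timed writing session, so someone who stops the first session early in distress is, on the natural reading, not shown it then

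*Protocol*

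**What the plan says.** The relevant text is in the Protocol, Section IV item 3 (Research Plan). The safety paragraph sits under the Control (C) Intervention heading but speaks of every participant, so it applies to all three arms. The program enforces the writing time "by not allowing the participant to advance until 20 minutes have passed". The support information follows: "After each writing session, participants will be provided with the contact information of a local mental health resource center". A research assistant reads each submission within 24 hours, and staff check the account daily and review participants' writing. A licensed clinical psychologist "will also contact participants who indicate threat to self or others or severe emotional distress".

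The reminder rules are under PHASE/AIM 3. For the first writing day, one email a day for three days is sent if the participant "has not begun their first writing day (Study Task 2) within 24 hours of receiving the prompt". The next step is: "If they still have not completed their writing prompt by the fifth day, then a research team member will try calling or texting" the participant. For the second day the trigger is worded differently: "If the participant does not complete the second writing day (Study Task 3) within 24 hours", staff use "the same email, text, and call reminder system as with writing day one". The third day follows the same procedure. Progress is sequential: "participants will not be invited to move on to the second writing prompt without first completing the prompt from writing day one".

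Section VII (Minimizing Risks) accepts that either active writing task may cause emotional discomfort and says that participants may stop at any time without penalty.

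**The concern.** Expressive writing asks for the participant's most stressful or traumatic LGBT+ related event. Self-affirmation writing asks participants to draw on their own experience of stigma. Stopping part-way through the first session is therefore a response that the protocol foresees and permits. The contact for outside help, as described, comes at the end of the session, and the session cannot be advanced for 20 minutes. The person most likely to need the contact on the first day may be the one who does not reach the point where it is given.

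The first-day email rule raises a second question. Someone who opened the task and left has begun it, so on a literal reading the emails do not apply to that person, although they would on days two and three.

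At stake is a simple participant protection. No power figure, estimate or test depends on it, and no direction of bias follows from it.

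**Working it through.** The protocol gives no figure to reproduce on this point, and no calculation applies. The check follows one participant through the described procedures: someone who opens Study Task 2 (the first writing session), writes for less than 20 minutes, and closes the page without submitting.

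1. **Resource contact.** It is tied to the end of a session, and the program does not allow advance before 20 minutes. The natural reading is that an early leaver does not reach it. The protocol does not expressly place the contact on a screen behind the timer, so this is an inference from the described order.
2. **24-hour review.** It covers submissions. This participant has submitted nothing.
3. **Daily account check.** It covers participants' writing. The protocol does not say whether unsubmitted text is visible to staff, so the check might or might not reveal the distress.
4. **Psychologist contact and staff referral.** Both depend on staff learning of the distress. The resource list in Section VIII item 1 is also held by staff.
5. **First-day emails.** There are two readings:
   - If the trigger means not begun, as written, this participant does not meet it.
   - If it means not completed, as on day two, the participant meets it and the first email arrives at about 24 hours.

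   Under either reading the emails are described only as encouragement to finish the writing. Nothing says that they carry the contact.
6. **Later sessions.** A participant is not invited to the second prompt without completing the first. Anyone who stops early on day two or three has therefore already been given the contact once, and the day-two and day-three triggers turn on completion. The question is confined to the first session.

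Steps 1 and 2 hold whichever way step 5 is read. The reminder wording affects only how soon someone writes to the participant, not whether the contact was shown.

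**The case against.** The strongest objection is that the deciding fact may lie outside the supplied text. Participants speak with trained staff at consent, and the protocol says that consent documents are attached. Those pages were removed before review, so contacts may already be given at enrolment. This stands. The point can say only where the supplied protocol text places the contact.

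The second objection is that the reminder wording is probably loose drafting. The first-day emails urge completion, the fifth-day sentence refers to people who have still not completed, the day-two process is called the same system as day one, and elsewhere reminders go to those who skipped a day. Read together, the rule most likely turns on completion. This also stands, and it reduces the wording difference to a clarification.

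Third, the reminders are adherence prompts. Changing the trigger alone would send someone who stopped in distress repeated requests to return to the task. This is correct, and it shapes the fix.

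Some stronger readings are tempting but unsupported:
- A reader might infer that an early leaver hears nothing until the fifth day. That takes the email trigger strictly and the fifth-day rule broadly. A consistently broad reading gives an email at about 24 hours, and a consistently strict one may not include the fifth-day call at all.
- A reader might infer that participants are held on the page. The timer blocks advancing; nothing says that it blocks leaving.
- A reader might count every first session in the active arms as exposed. That would be true only if everyone stopped early.
- A reader might infer that distressed participants have no support. The daily check, psychologist contact, trained staff and staff-held resource list all count against that.

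**Conclusion.** The point holds as a minor, inexpensive safety improvement. As described, the contact follows the session, the session cannot be advanced for 20 minutes, and the 24-hour review covers submissions. A first-session participant who stops early is therefore, on the natural reading, not shown the contact at that moment and leaves no submission to review. The differing first-day trigger is a secondary wording matter that is probably unintended.

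The conclusion rests on two assumptions: that provision after a session means after the timed page, and that nothing in the removed consent pages already supplies the contact. If contacts are given at enrolment, the change only repeats them where they are most useful. The documents give no rate of early stopping, so the number of people affected cannot be estimated. The protocol rates the study as minimal risk, and this point does not contradict that rating.

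**What to change.** Keep the 20-minute timer and make three small changes:

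1. Show the existing mental health contact before or on the writing page, identically in all three arms, as well as after the session.
2. Reword the first-day email trigger to not completed within 24 hours, matching day two.
3. Make change 2 only together with an added line in the reminder that gives the contact and says that stopping is allowed. Without that line, the new trigger would simply press a distressed person to resume.

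The cost is a small change to platform and reminder text, an IRB wording amendment, and a few extra emails and replies to handle. At three daily emails, that is up to three more for each person who starts the first session and does not finish, if staff now apply the literal wording. Showing the contact and the permission to stop may slightly lower the number of completed sessions; using the same display in every arm keeps the comparison even. No extra participants are needed.

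As an option outside the safety point, sessions started but not submitted could be reported by arm, where the platform records them. That would be useful acceptability data in a phase powered mainly for feasibility and acceptability (Section V item 4).
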